## **8.11. Efficacy Analyses**

### **8.11.1. Analysis of Primary Efficacy Endpoints**

The primary efficacy endpoint for this study is the proportion of patients with an overall success (clinical cure and microbiologic eradication) in the m-MITT Population at the TOC Visit.

Patients will be programmatically categorized as a success, failure, or indeterminate response. Patients with missing data or who are lost to follow-up are defined as indeterminate for the primary analysis and are included in the denominator for the calculation of overall success rate. Thus, patients with an indeterminate outcome are considered failures for the primary analysis. The number and percentage of patients in each treatment group in each response category will be reported.

The proportion of patients with overall success will be summarized by treatment group in the m-MITT and ME Populations. Two-sided 95% CIs will be presented for the observed difference in the overall success rate (EXT2514SUL group minus placebo group [background imipenem/cilastatin therapy]). The primary analysis is based on a CI computed using a continuity-corrected Z-statistic.

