9.2 Statistical Methods

The efficacy analyses will be descriptive summaries. Descriptive statistics, including the numbers and percentages for categorical variables, and the numbers, means, standard deviations, medians, minimums, and maximums for continuous variables will be provided. All comparisons will be for ETX2514SUL versus placebo. Listings of individual patient data will be produced. A complete analysis of efficacy and safety data will be performed and detailed in the SAP.

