9.2.2.1 Primary efficacy analysis

The primary efficacy endpoint for this study is the proportion of patients with an overall success (clinical cure and microbiologic eradication) in the m-MITT Population at the TOC Visit.

Patients will be programmatically categorized as a success, failure, or indeterminate response. Patients with missing data or who are lost to follow-up are defined as indeterminate for the primary analysis and are included in the denominator for the calculation of overall success rate. Thus, patients with an indeterminate outcome are considered failures for the primary analysis. The number and percentage of patients in each treatment group with an overall success, failure, and indeterminate response will be determined. A 2-sided 95% confidence interval (CI) for the observed difference in the overall success rates (EXT2514SUL group minus placebo group [background imipenem/cilastatin therapy]) will be calculated using a continuity-corrected Z-statistic.

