#### **4. SAMPLE SIZE DETERMINATION**

Overall, the study is anticipated to randomize approximately 80 patients in a 2:1 ratio to receive ETX2514SUL or placebo. No formal power calculations have been performed for this study. The sample size is based on practical considerations.

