### **7.3. Microbiologically Modified Intent-to-Treat Population**

The Microbiologically Modified Intent-to-Treat (m-MITT) Population will include patients who meet MITT criteria and have at least 1 baseline uropathogen from an appropriately collected pre-treatment baseline urine or blood sample. To be considered a pathogen, the baseline urine culture must grow 1 or 2 bacteria isolates, each at  $\geq 10^5$  CFU/mL. If  $\geq 3$  bacterial isolates are identified, the culture will be considered contaminated regardless of colony count unless 1 of the isolates, even if the CFU/mL is  $< 10^5$ , that grows in the urine is also isolated from a blood culture obtained within 48 hours before the start of administration of the first dose of study drug. If the same pathogen is present in both blood and urine cultures, even if the CFU/mL is  $< 10^5$  in the urine, the organism will be considered a pathogen.

The m-MITT Population will be the primary efficacy population.

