# **8. STATISTICAL ANALYSIS**

## **8.1. General Statistical Considerations**

Summary statistics will be presented by treatment group. For continuous variables, the number of observations (n), mean, standard deviation, median, minimum, and maximum will be provided. For categorical variables, the frequency and percentage in each category will be displayed.

For summary statistics, the mean and median will be displayed to one decimal place greater than the original value and the measure of variability (e.g. standard deviation) will be displayed to two decimal places greater than the original value. All analyses will be performed using SAS® Version 9.3 or higher.

Descriptive statistics will be provided for each treatment group (ETX2514SUL and placebo [background imipenem/cilastatin therapy]). Statistical tests and/or confidence intervals (CIs) will be used to compare treatment groups.

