### **8.11.2. Additional Analyses of the Primary Efficacy Endpoint**

The primary efficacy outcome will also be assessed separately across the randomization stratification factor of baseline diagnosis (symptomatic cUTI versus AP) for the m-MITT Population. For each baseline diagnosis stratum, a 95% CI will be computed for the difference in the overall success rate using a continuity-corrected Z-statistic. Exploratory analyses in other subgroups may also be conducted.

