### **8.11.3. Analysis of Secondary Efficacy Endpoints**

The number and percentage of patients determined to be a clinical cure, clinical failure and indeterminate response at the TOC visit in the MITT, m-MITT, CE and ME Populations will be presented by treatment group. Two-sided 95% CIs for the observed difference in the clinical cure rates between the EXT2514SUL group and the placebo group (background imipenem/cilastatin therapy) will be presented based on a continuity-corrected Z-statistic.

The number and percentage of patients with a per-patient microbiologic eradication, persistence, and indeterminate response at the TOC Visit in the m-MITT and ME Populations will be presented by treatment group. Two-sided 95% CIs for the observed difference in the per-patient microbiological eradication rates between the EXT2514SUL group and the placebo group (background imipenem/cilastatin therapy) will be presented based on a continuity-corrected Z-statistic.

[Redacted content]

  

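### The continuity-corrected Z interval suits the small pyelonephritis stratum poorly: it is wider than a score interval there and, at unequal high success rates, can also cover well below 95%

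*SAP*

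**What the plan says.** The same method appears in four places.

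- SAP 8.11.1, overall success in the m-MITT Population: "The primary analysis is based on a CI computed using a continuity-corrected Z-statistic".
- SAP 8.11.2, by randomisation stratum: "For each baseline diagnosis stratum, a 95% CI will be computed for the difference in the overall success rate using a continuity-corrected Z-statistic".
- SAP 8.11.3, clinical cure and microbiologic eradication: intervals "will be presented based on a continuity-corrected Z-statistic".
- Protocol 9.2.2.1, and likewise the synopsis: the primary interval "will be calculated using a continuity-corrected Z-statistic".

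Neither document states the variance form, the size of the correction, or what happens when an arm is at 100%. Text after SAP 8.11.3 is redacted and is not counted as missing here.

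The setting is about 80 patients randomised 2:1, with at least 30% having AP (SAP 3.2 and 4). The primary efficacy population keeps only treated patients who "have at least 1 baseline uropathogen from an appropriately collected pre-treatment baseline urine or blood sample" (SAP 7.3). On purpose and size, Protocol 9.2 says "The efficacy analyses will be descriptive summaries" and SAP 4 says "No formal power calculations have been performed for this study".

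**The concern.** A continuity correction is normally defended as safe: the interval is a little wide, but it holds its level. That defence is reasonable for about 80 patients. It is weaker in a stratum of about 24 split 16:8. There the correction adds more than 9 points to each side, while the Wald standard error shrinks towards zero as an arm approaches 100% success. The interval can then be too wide at moderate rates and too short in the wrong samples at high rates.

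At stake is how the stratum results will be read. A reader takes the stated 95% at face value. If every AP patient succeeded, the planned interval would suggest a precision that 24 patients cannot provide.

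**Working it through.** The documents give no interval width, success rate or margin, so there is no plan figure to reproduce.

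**Inputs**
- Overall: 80 at 2:1, about 53:27 (SAP 4), taking all 80 as m-MITT.
- AP at its floor: 0.30 × 80 = 24, or 16:8. This leaves 56 with cUTI, or about 37:19. AP may exceed its floor, and m-MITT will reduce the numbers.
- Success rates (assumed): equal rates of 0.70-0.85, plus a grid of 876 pairs with both rates from 0.60 to 0.95 in steps of 0.01, differing by at most 0.15.

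**Formulas**
- Planned interval (assumed Wald form): d ± [1.96 √(p1q1/n1 + p2q2/n2) + 0.5(1/n1 + 1/n2)], with d = p1 − p2 and limits cut at ±1. A pooled-variance form was checked as well.
- Miettinen-Nurminen (MN): all δ with |d − δ| ≤ 1.96 √V(δ). V(δ) is the variance at the maximum-likelihood rates constrained to differ by δ, multiplied by N/(N − 1).
- Expected width and coverage come from full enumeration of both binomials, without simulation.

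**Size of the correction, per side**
- 53:27: 0.5(1/53 + 1/27) = 0.028
- 16:8: 0.5(1/16 + 1/8) = 0.094

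**AP stratum, 16:8** (first rate is the ETX2514SUL arm)

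| True rates | Planned width | MN width | Planned coverage | MN coverage |
|---|---|---|---|---|
| 0.70 vs 0.70 | 0.916 | 0.722 (planned 27% wider) | 96.4% | 96.0% |
| 0.85 vs 0.85 | 0.736 | 0.650 (planned 13% wider) | 99.0% | 96.7% |
| 0.95 vs 0.85 | 0.646 | 0.602 | 86.6% | 95.2% |
| 0.95 vs 0.80 | 0.710 | 0.610 | 82.7% | 97.0% |

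In the last two rows the planned interval is wider and also covers less. One patient matters: at 16:7 and 0.95 vs 0.85 its coverage is 99.2%, while MN moves only from 95.2% to 96.3%. At 24:12 and the same rates the planned interval covers 90.7%.

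**How widespread the shortfall is**

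| Sizes | Planned: minimum | Planned: below 95% | MN: minimum | MN: below 95% |
|---|---|---|---|---|
| AP 16:8 | 82.7% | 9.4% of pairs | 93.4% | 14.6% |
| cUTI 37:19 | 90.9% | 1.9% | 93.8% | 26.5% |
| Overall 53:27 | 93.6% | 0.2% | 94.4% | 30.3% |

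At 16:8 the planned interval is below 90% at 14 of 876 pairs (1.6%). All 14 have the larger arm at 0.90 or above and the smaller arm at least 10 points lower. With pooled variance the 16:8 minimum is 87.8%.

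**All 24 AP patients succeed.** The standard error is zero, so the limits are 0 ± 0.094, or ±9.4 points. MN gives −20.0 to +33.4 points. The chance of this is 0.80^24 = 0.5% at a rate of 0.80 and 0.90^24 = 8% at 0.90.

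**Overall, 53:27, equal rates 0.70-0.85.** Planned coverage is 96.6-97.2%. Expected width falls from 0.473 to 0.378, against 0.415 to 0.343 for MN. The ratios are 0.473/0.415 = 1.14 and 0.378/0.343 = 1.10.

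**The case against.** The strongest reply has four parts.

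- **The comparison is a trade-off.** The score interval holds 95% on average, not as a minimum, and over the grid it is below 95% more often than the planned one. Its shortfalls are shallow and the planned interval's are rarer but deeper. This stands, and for the overall interval it makes replacement a matter of preference. In AP it does not rescue the planned interval, which can fall to 82.7% while also being wider.
- **The figures rest on an assumed formula.** This stands. With a smaller correction, 1/(2 × smaller arm), and n − 1 variances, the overall excess width is 6-11%. If the corrected statistic is inverted with a constrained variance, 16:8 coverage stays at about 98% or more over the grid, and the all-success case gives roughly −33 to +45 points. The under-coverage then disappears and excess width remains. The choice of formula therefore matters enough to be written down.
- **Rates near 0.95 may not occur.** Indeterminate outcomes count as failures (SAP 8.11.1), which lowers the composite success rate. This also stands: with both rates at most 0.90, the 16:8 minimum is 89.2%.
- **Little depends on it.** Efficacy is descriptive and safety is the primary objective.

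A reader might go further and infer that the primary efficacy interval is invalid, or that both strata are equally affected. The coverage figures for 53:27 and 37:19 do not support either. Nor can the interval be called the only comparative method, since SAP 8.1 says "Statistical tests and/or confidence intervals (CIs) will be used to compare treatment groups".

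**Conclusion.** The point holds for the AP stratum in SAP 8.11.2. Under the Wald form at 16:8, the planned interval gives up 13-27% in width at equal rates of 0.70-0.85. At unequal rates near the boundary it can also cover only 83-87%. The problem is milder with pooled variance and milder in cUTI.

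For the overall interval the conclusion is narrower. It is conservative at moderate rates and dips below 95% only close to the boundary, so the cost is 10-14% in width. That figure assumes all 80 patients are in m-MITT; at 40:20 the excess is 11-17%.

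The success rates, the m-MITT size and the formula are assumptions; only the absence of a written formula does not depend on them. The impact is modest, because no margin, power calculation or decision rule uses these intervals.

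**What to change.** In SAP 8.11.2, report a Miettinen-Nurminen score interval for the risk difference within each diagnosis stratum. Keep the continuity-corrected interval there as a sensitivity analysis, and state its variance form, its correction, and its limits when an arm is at 100%. The same formula statement serves SAP 8.11.1 and 8.11.3.

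Optionally, show the score interval beside the planned one for the overall primary and secondary comparisons. The planned overall interval can stay as it is.

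The cost is a wording change in the SAP before unblinding and a few lines of code, with no new data or patients. Protocol 9.2.2.1 names the method only for the overall primary interval, so the stratum change needs no protocol amendment. The downside is that the score interval does not guarantee 95%: at 16:8 it is slightly below at about 15% of the rate pairs examined (minimum 93.4%). If it is also shown overall, the figure is about 30% (minimum 94.4%).

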## 3. STUDY DESIGN

### 3.1. General Study Design and Plan

This study is a double-blind, randomized, placebo-controlled study to evaluate the safety and efficacy of intravenous (IV) ETX2514SUL in patients with cUTIs who are otherwise relatively healthy. Patients providing informed consent and meeting all study eligibility criteria will be enrolled in the study and have a pre-treatment urine and blood sample obtained and submitted to the local laboratory. Approximately 80 patients will be randomized 2:1 to receive either 1 g ETX2514/1 g sulbactam IV or matching placebo every 6 hours (q6h). All patients will receive background therapy with 500 mg IV imipenem/cilastatin q6h. Randomization will be stratified by baseline diagnosis (symptomatic cUTI versus AP). At least 30% of patients will have a diagnosis of AP at study entry.

Receipt of any long-acting, potentially-effective systemic antibiotic with activity against Gram-negative uropathogens for more than 24 hours within the 72-hour window prior to randomization is prohibited. However, patients who have received a single dose of a short-acting systemic antibiotic up to 24 hours prior to randomization may be randomized up to a maximum of 25% of the study enrollment. A short-acting antibiotic is defined as having a dosage frequency of more than once daily (eg, every 12 hours or more frequently).

Any organism isolated from the blood or urine cultures will be identified by genus and species by the local laboratory. Urine organisms will be cultured and quantified at the local laboratory, and

susceptibility of the organism(s) may be performed per local laboratory standards. All baseline urine organisms that grow  $\geq 10^5$  colony-forming units (CFU)/mL and not deemed to be a contaminant, as detailed in the Microbiology Procedures Manual, are to be sent from the local laboratory to the central laboratory. Potential pathogens that grow in both the urine and blood will also be sent to the central laboratory prior to randomization.

For post-baseline urine cultures, only those potential pathogens that grow at  $\geq 10^3$  CFU/mL and deemed not to be contaminants will be sent to the central laboratory.

All blood organism(s) cultured at the local laboratory from blood samples (whether at baseline or post-baseline) and not deemed to be a contaminant per the Microbiology Procedures Manual will be sent to the central laboratory for confirmation of identification and susceptibility testing.

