### **3.2. Study Population**

The population for this study is approximately 80 hospitalized adult patients with cUTI, including AP. At least 30% of patients will have a diagnosis of AP at study entry.

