### **3.3. Randomization and Blinding**

Qualifying patients will be randomized in a 2:1 ratio to receive 1 g ETX2514/1 g sulbactam or placebo via the Interactive Response Technology (IRT) system. All patients will receive 500 mg IV imipenem/cilastatin q6h.

Randomization will be stratified by baseline diagnosis (symptomatic cUTI versus AP). A manual will be provided that describes the IRT system and includes user instructions.

At least 30% of patients will have a diagnosis of AP at study entry.

Patients who have received a single dose of short-acting antibiotic (see Protocol Appendix C for a list of allowed and disallowed antibiotics) for cUTI or AP within 24 hours of randomization will comprise a maximum of approximately 25% of the study enrollment. Patients who have received any potentially therapeutic and long-acting antibiotic for more than 24 hours within the 72-hour window of the start of administration of the first dose of study drug will be excluded from the study.

A randomization notification will be sent to the unblinded pharmacist (or appropriately qualified unblinded designee) at the site. A blinded randomization notification will be sent to the appropriate blinded site personnel.

The Investigator, site personnel, Sponsor, and the Sponsor's designees involved in monitoring, data management, and other aspects of the study will be blinded to treatment assignment. An unblinded site monitor will be assigned to review unblinded pharmacy data and will follow documented procedures to ensure that the blind is maintained throughout the study.

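### Randomization is stratified by cUTI versus AP, but the overall primary and secondary intervals are for crude differences and no stratum-adjusted overall difference is planned (minor)

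*SAP*

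**What the plan says.** SAP 3.3 sets one stratification factor with two levels: "Randomization will be stratified by baseline diagnosis (symptomatic cUTI versus AP". Protocol 5.3 says the same. Neither gives a reason for the choice.

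For the primary endpoint (overall success at TOC in m-MITT), SAP 8.11.1 says "Two-sided 95% CIs will be presented for the observed difference in the overall success rate", and then "The primary analysis is based on a CI computed using a continuity-corrected Z-statistic". Protocol 9.2.2.1 agrees: the interval "will be calculated using a continuity-corrected Z-statistic". Neither text mentions a stratum term or weights. SAP 8.11.3 applies the same method to clinical cure (MITT, m-MITT, CE, ME) and to microbiologic eradication (m-MITT, ME).

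In the visible efficacy analyses, the stratum is used only in SAP 8.11.2: "The primary efficacy outcome will also be assessed separately across the randomization stratification factor of baseline diagnosis". This gives one interval per stratum, for the primary endpoint in m-MITT. It does not combine them. Text following the secondary analyses in SAP 8.11.3 is redacted, so the absence of an adjusted analysis can be asserted for the visible text only.

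**The concern.** Stratified randomization keeps the AP share close in the two arms among all randomized patients. The primary population is narrower. m-MITT requires a qualifying baseline pathogen (SAP 7.3), and CE and ME add dosing and evaluability conditions (SAP 7.4, 7.5). The AP share can therefore drift apart between arms in these sets.

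If success also differs by diagnosis, part of a crude treatment difference is then a diagnosis difference. A stratum-weighted estimate removes that part at almost no cost. If it is not prespecified, any adjustment made after an imbalance has been seen is post hoc.

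**Working it through.** **Inputs from the documents**
- "Approximately 80 patients will be randomized 2:1 to receive either" (SAP 3.1): 80 × 2/3 ≈ 53 active and 27 placebo.
- "At least 30% of patients will have a diagnosis of AP at study entry" (SAP 3.2). No upper limit is given, so 30% and 50% are used.
- "No formal power calculations have been performed for this study" (SAP 4), so there is no planned figure to reproduce.

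**Assumptions, not in the documents**
- Retention in m-MITT is 80% in both strata, with 60% as a harsher case.
- Success rates are as listed below, with no true treatment effect.
- The planned interval is d ± [1.96·SE + ½(1/n₁ + 1/n₀)], with unpooled SE. The documents do not write the formula out.

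**Step 1: size of the planned interval.** At 80% retention, n₁ = 42 and n₀ = 22, so 1/42 + 1/22 = 0.0693. With 80% success in both arms, SE = √(0.16 × 0.0693) = 0.1053. The half-width is 1.96 × 0.1053 + 0.0346 = 0.241, or 24.1 points.

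**Step 2: how imbalance enters.** With no treatment effect, the expected crude difference is (AP share, active − AP share, placebo) × (success in AP − success in cUTI). Take an illustrative m-MITT set with 16 of 42 active and 6 of 22 placebo patients having AP, and success of 90% in AP and 70% in cUTI:
- active: (16 × 0.9 + 26 × 0.7)/42 = 77.6%
- placebo: (6 × 0.9 + 16 × 0.7)/22 = 75.5%
- crude difference: 2.2 points, which equals the share imbalance of 10.8 points × 0.20

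The Mantel-Haenszel difference is Σwₖdₖ/Σwₖ with wₖ = n₁ₖn₀ₖ/(n₁ₖ + n₀ₖ). The weights here are 4.4 for AP and 9.9 for cUTI. Each dₖ has expectation zero, so the weighted difference does too.

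**Step 3: simulation at 80% retention** (100,000 trials per row; all results in points or %)

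| AP share | Success AP/cUTI | Imbalance, 95th pct | Shift, 95th pct | Planned half-width | Planned coverage | MH + same correction: half-width | Its coverage | Uncorrected stratified Wald coverage |
|---|---|---|---|---|---|---|---|---|
| 30% | 80/80 | 11.1 | 0 | 23.7 | 96.8 | 23.4 | 96.5 | 92.7 |
| 30% | 85/75 | 11.2 | 1.1 | 24.5 | 96.8 | 24.1 | 96.5 | 93.0 |
| 30% | 90/70 | 11.1 | 2.2 | 25.2 | 97.0 | 24.4 | 96.5 | 93.1 |
| 50% | 80/80 | 13.2 | 0 | 23.8 | 96.8 | 23.4 | 96.6 | 92.9 |
| 50% | 85/75 | 13.2 | 1.3 | 23.8 | 96.9 | 23.2 | 96.4 | 92.6 |
| 50% | 90/70 | 13.2 | 2.6 | 23.8 | 97.2 | 22.8 | 96.5 | 92.8 |

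In the 50% rows, about 2.8 points of imbalance come from rounding 2:1 within strata (27/53 − 13/27). At 60% retention, the 95th percentile of imbalance is 18.1 to 20.7 points. The shift is then up to 4.1 points for a 20-point gap, against a half-width of 28.0 to 29.7.

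**Step 4: trials with a marked imbalance** (80% retention, gap of 15 to 30 points). The AP share differs by at least 8 points, in either direction, in 15 to 19% of trials; it favours the active arm in about 9%. In those, the crude difference averages about +1.5 to +3.4 points. The Mantel-Haenszel difference stays within 0.4 points of zero.

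**Step 5: overall precision.** Root mean squared error, crude versus Mantel-Haenszel, at 30% and 50% AP:
- 85/70: 11.45 vs 11.45, and 11.07 vs 11.05
- 90/60: 11.84 vs 11.75, and 11.06 vs 10.92
- equal rates: 10.59 vs 10.61

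**Step 6: interval for the fix.** Among score (Miettinen-Nurminen) intervals, stratifying gave coverage of 95.0 to 95.2%, against 95.3 to 96.2% unstratified. Width was 0 to 3% narrower when strata differ and 0.3% wider when they do not. This compares two score intervals; neither is the planned one.

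**The case against.** The case for leaving the plan alone is strong on size.
- **No decision depends on the interval.** Safety is the primary objective, Protocol 9.2 calls the efficacy analyses descriptive, and there is no margin or power calculation. This stands, and it sets the priority.
- **The effect is small.** The 1.5 to 3.5 points apply only when a marked imbalance favours the active arm, and only under an assumed gap. With no gap the shift is zero. This stands.
- **Much is already visible.** SAP 8.7 tabulates infection type in each population, and SAP 8.11.2 gives per-stratum differences, which a reader could reweight. This stands in part. At 30% AP and 80% retention the AP stratum has about 13 versus 6 patients (16 × 0.8 and 8 × 0.8). The secondary endpoints get no per-stratum results in the visible text.

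A reader might infer that the sponsor stratified because success is expected to differ by diagnosis. The documents never say so. A reader might also extend the culture-selection argument to every secondary interval. It does not reach clinical cure in MITT, which keeps every randomized patient who received any study drug (SAP 7.2).

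**Conclusion.** The gap is real but minor. The visible plan stratifies randomization by diagnosis and then gives no stratum-adjusted overall difference for the primary or secondary endpoints. Under the stated assumptions, an imbalance of at least 8 points toward the active arm shifts the crude difference by about 1.5 to 3.5 points, against a half-width of about 24 to 27.

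It would be tempting to call the primary interval biased or invalid. The calculations do not support that: coverage is about 97%, and the shift matters only conditionally on an imbalance. Nor is there a real efficiency argument, since precision improves by about 0 to 1%. What remains is an inexpensive way to remove a conditional distortion using the factor the trial already randomizes by. The size rests on assumed retention, AP share and success rates, none of which the documents give.

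**What to change.** Before unblinding, add to SAP 8.11.1 and 8.11.3 a Mantel-Haenszel-weighted risk difference across the two randomization strata, with a stratified Miettinen-Nurminen 95% CI. Do not use an uncorrected stratified Wald interval, whose coverage at this size is 91.5 to 93.1% across the scenarios run. State that a stratum with no patients in one arm receives zero weight.

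Two placements are acceptable:
- Report it beside the planned crude continuity-corrected interval. This needs SAP wording only.
- Make it the main estimate and keep the crude interval as supportive. Protocol 9.2.2.1 must then be aligned, which means an amendment.

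Keep SAP 8.11.2 as it is. The cost is a few lines of standard code and some extra output, with no new data or patients. If the strata have equal success rates, the loss of precision is negligible (about 0.02 points of root mean squared error).
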